## I. Hypotheses and Specific Aims:

The overarching hypothesis of this work is that the lack of shared decision making (SDM) for prosthetic design and failure to match patient expectations with a prosthetic design plan result in poor health outcomes for patients with LLA. Shared decision making (SDM) is where clinicians and patients share the best available evidence for comparing options in order to achieve informed preferences for making health decisions. A patient's involvement in their health care process is known to affect their satisfaction,  adherence to care programs,  and health outcomes.  **Clinical** decision aids (DAs) support patients in SDM and making informed health decisions, by providing information on the available options and associated outcomes. 6 DAs are intended to help patients clarify their values associated with the options and potential outcomes, to create a platform for communication with healthcare providers. DAs have been shown to improve patient knowledge and realistic expectations for given health options. This project aims to examine how to better align patient and clinician values and expectations by developing a DA for prosthetic design decision options, to support SDM between patients receiving their first prosthesis and prosthetic care providers. This proposal will be guided by the International Patient Decision Aids Standards (IPDAS).6-8

**Aim 1:** Qualitatively define the key determinants and decisional needs of new prosthetic patients (n=14) and prosthetic care providers (n=20- 24) during prosthetic design, via semi structured interviews with patient participants and focus groups with prosthetist participants.

Expected Result 1.1: Key determinants and decisional needs for prosthetic design will be defined using content analysis guided by the Ottawa Decision Support framework for patients making health decisions, and the Model for Shared Decision Making in Clinical Practice.

Expected Result 1.2: Key stakeholders who contribute directly to prosthetic design decisions (e.g., patients with LLA, prosthetists, physicians, caregivers, close friends or family members) will be identified via purposive sampling, to inform the target end users of a DA prototype.

**Aim 2:** Synthesize the evidence for prosthetic design decision options to develop a DA prototype.

Expected Result 2.1: Via systematic literature review, a DA prototype will be developed from the evidence on prosthetic design decision options associated with decisional needs identified in *Aim 1*.

**Aim 3:** Assess the DA prototype's accuracy, comprehensibility, and usability through alpha testing with an **expert working group** of patients with LLA and prosthetic care

providers.

Expected Result 3.1: Quantitative results from a Likert scale measurement of the DA prototype's accuracy, comprehensibility and usability will inform revisions to the DA prior to use in a pilot clinical trial.

Expected Result 3.2: Qualitative feedback on the DA prototype's accuracy, comprehensibility, and usability will inform directed iterative revision for the DA prototype and implementation methods for use in a pilot clinical trial.

## II. Background and Significance:

This proposal addresses three significant problems with conventional prosthetic design: 1) suboptimal patient outcomes after LLA; 2) challenges in the prosthetic design process that limit SDM; and 3) under-informed expectations for function with a prosthesis for patients and prosthetic care providers.

# 2.1. High cost and suboptimal patient health and rehabilitation outcomes after LLA

LLA is a high cost, chronic health condition marked by poor health-related outcomes. 11-17 Five-year health care and prosthetic costs after amputation are estimated to be more than triple the lifetime health-care cost of an average person. 16 In spite of the high cost and high resource allocation after LLA, strong evidence demonstrates a decline in functional outcomes, such as physical capacity (strength and balance), and walking ability (velocity and symmetry). 18-20 Psychosocial outcomes (e.g., quality of life, depression) are also lower in people after LLA when compared to general population

norms. When physical function and psychosocial outcomes are evaluated in combination, up to half of patients are unable to achieve their pre-amputation levels of mobility and quality of life one year after LLA. Thus, successful rehabilitation after LLA is multidimensional.

[figure not shown]

Figure 1. Conceptual framework linking Shared Decision Making and patient outcomes, adapted from Shay et al. 21

involving many interrelated aspects of health outcomes. It is also unclear how health outcomes are affected by patient expectations and patient involvement in prosthetic design decisions. **Shared Decision Making (SDM)** is a process of supported patient and clinician communication to identify patient values and inform expectations about potential health options, and has been shown to improve patient satisfaction and adherence to care plans. SDM offers a solution for improving health-related outcomes after LLA through a mechanism of affective-cognitive (knowledge and understanding of options) and behavioral outcomes (adherence to care plans and adoption of health behaviors) (**Figure 1**). This proposal aims to improve the complex combination of both physical function and psychosocial outcomes of patients with LLA by supporting SDM in the prosthetic design process.

## 2.2. Prosthetic design challenges that limit SDM

One challenge in the prosthetic design process is the variety in patient characteristics that can be difficult to align with abundance of prosthetic design options available to choose from. Prosthetic deisgn options offer a range in technology, appearance,

functional performance, expense, maintenance, method of use, safety, and stability.  Components of the prosthetic design decision include selecting a prosthetic socket, interface, suspension system, components, and cover (**Table 1**). For example, prosthetic interfaces (e.g., gel, urethane, silicone) between the residual limb and the prosthetic socket may provide increased comfort and protection for bony prominences, however are also associated with increased cost, maintenance, and may be difficult to donn. Additionally, several patient-specific factors may influence prosthetic component selection (**Table 2**); for example, a patient with limited hand dexterity may benefit from a prosthetic suspension system that is easy to donn over a system that requires more upper extremity strength, such as a pin locking gel liner.

However, gel liners may be more ideal for patients with high activity levels, due to the skin protecting features and reduced shear forces on the residual limb. Higher costing prosthetic design options tend to be associated with more advanced appearance, materials, technology, safety

Key Decision: Prosthetic Design	
Decision Components	Potential Decision Options
Prosthetic Socket	Total surface bearing, patellar tendon
	bearing, ischial containment,
	quadrilateral socket
Prosthetic Interface	Sock, gel, silicone, urethane, foam
Prosthetic Suspension	Suction, pin, lanyard, sleeve, belt
Prosthetic Components	Prosthetic foot, knee
Prosthetic Cover	Foam, protective skin, no cover

Table 1. Potential Prosthetic Design Subcomponents & Decision Options

features, and greater user satisfaction, yet may be resisted by health-care financers, or be less than ideal in certain environments (maintenance, sweat management, access to electricity for charging, less resistant to water exposure). In order to optimize prosthetic design, prosthetic care providers are challenged with combining the best available evidence around prosthetic design options, their clinical expertise, patient-specific factors, and patient values. The most appropriate option for a given patient is often unclear, and matching the optimal prosthetic option to a patient's need and potential remains difficult. The tradeoffs in the prosthetic design decision making process emphasize the need for decision support for both patients and prosthetic care providers. 28,34

Challenges in the prosthetic design process contribute to a lack of SDM between patients with LLA and their healthcare providers. In the general population, most patients prefer to be active partners in decisions about their healthcare.  Effective SDM between patients and health care providers is associated with greater patient satisfaction with care processes, adherence to treatment programs, improved self-reported health, and overall informed expectations.  However, patients with LLA assume passive roles in the prosthetic design process due to a lack of knowledge and experience necessary to collaborate in prosthetic decisions.  Discussing options and recognizing patient preferences is acknowledged as an important factor in improving prosthetic use and adherence to care plans, even when options are limited.  The proposed project aims to improve the exchange of information about prosthetic design options between patients and their prosthetic care providers, in order to align values with prosthetic design decisions.

## 2.3. Under-informed patient and prosthetic care provider expectations

Both patient and prosthetic care provider expectations around anticipated function with a prosthesis are under-informed. Patients with LLA do not know what to expect from their first prosthesis, and their expectations for returning to pre-amputation levels of

function after LLA are often unrealistically high. 38,39 The tendency for patients to believe that parts of a prosthesis determine their ability to walk rather than their own physical ability is a prevalent concern among prosthetic care providers. Prosthetic care providers also express difficulty predicting patient health outcomes with a prosthesis, further contributing to the ambuiguity of both patient and clincian expectations for prosthetic rehabilitation. The lack of informed expectations may potentially link to reported low levels of patient satisfaction for function with a prosthesis, 40,41 and prosthetic non-use rates by patients as high as 15%. 42 Thus, managing unrealistic patient expectations in the prosthetic design process is a difficult endeavour and often viewed negatively in prosthetic care. In other populations, patient expectations for a given outcome are associated with success in rehabilitation, adherence to care plans, and improved functional recovery. 5,43-45 In a review on patient expectations after a surgical intervention, patients whose functional expectations were fulfilled had higher gains in satisfaction and physical quality of life. 45-47 In contrast, patients with unrealistic expectations for a given outcome after a health event may become discouraged and fail to meet their maximum potential. In order to achieve patient satisfaction with prosthetic care, a patient's expectations for a prosthesis must align with their experience. We hypothesize that the failure to match patient expectations with a prosthetic design plan result in poor health-related outcomes for patients with LLA. The proposed project aims to inform realistic patient expectations during the prosthetic design process, to improve health-related outcomes after LLA.

# III. Preliminary Studies/Progress Report:

Existing research has identified that **DA** address problems in conventional healthcare by: **1)** improving patient health outcomes by providing high quality information on the available prosthetic design options and associated outcomes; **2)** supporting patients and care providers in identifying and discussing values associated with healthcare options and reducing decisional conflict; and **3)** aligning patient and care provider goals and values to inform expectations for healthcare options.

## 3.1. Decision Quality: DA to improve LLA health outcomes

The relationship between patient health outcomes after LLA and SDM has yet to be explored. A potential mechanism for improving health-related outcomes after LLA is through SDM by means of improving patient knowledge and understanding of prosthetic design options. DAs are designed to support patients and healthcare providers in SDM by providing high quality information on available decision options, and have been shown to improve patient knowledge of options by as much as 20%. Through the development and use of an innovative DA for prosthetic design, patients with LLA will gain new access to knowledge (high quality evidence) necessary to participate in decision making for their prosthesis. Upon completion, this proposal will be positioned to examine patient knowledge of prosthetic design options in concordance with patient health outcomes.

# 3.2. Quality of Decision Making: Increase SDM and reduce decisional conflict in prosthetic design

The proposed study will introduce SDM to the prosthetic design process using a novel DA to promote discussion of prosthetic design options, thus reducing decisional conflict. SDM has been shown to help patients make informed decisions that are in line with their

goals and values,  and can be valuable for situations where evidence is insufficient or when personal preferences heavily influence the decision.  Furthermore, the use of DAs has been shown to increase the likelihood of discussing potential decisions, patient participation, and decrease decisional conflict by up to 10%.  Given the problem of limited patient participation in prosthetic design decisions, this proposal offers a solution for improving the quality of decision making in the prosthetic design process by supporting SDM between prosthetic care providers and patients. This proposal will also explore methods for implementing the use of a DA and identify areas for training on SDM in the prosthetic design process.

# 3.3. Decision Quality: Align patient and prosthetic care provider values to inform expectations

The proposed study will create and test a DA that improves values-treatment concordance for prosthetic design decisions in order to create realistic expectations for selected prosthetic options. This is important, as it will translate directly to clinical practice by helping patients construct and communicate personal values associated with the different options. A crucial aspect of the proposed study is the solution for uninformed patient and prosthetist expectations by means of a DA, to create a platform for aligning both patient and provider values (the benefits or risks that matter most) around the potential options, thus creating more realistic expectations for the outcome of each option. DAs have been shown to improve the congruency between the decision and patients' values by as much as 51%, and improve realistic expectations of option outcomes by as much as 82%. The proposed study will create a DA that is a new and innovative approach to improving values-treatment concordance for prosthetic design decisions, in order to create realistic expectations for selected prosthetic options.

## IV. Research Methods

## A. Outcome Measure(s):

## A.1. Aim 1: Qualitative Scoping Outcome Measures

Semi-structured interviews with participants with LLA will be conducted by a trained qualitative interviewer using video web conferencing with audio recording. Video conferencing will provide the benefits of in-person interviews (e.g., developing rapport, increasing accuracy, adding validity) while reducing participant travel burden. One-on-one semi-structured interviews with participants with LLA provide the opportunity for the interviewer/interviewee to diverge and pursue an idea or response in more detail (i.e., discussion of personal values associated with prosthesis design). Therefore, one-on-one semi-structured interviews provide the greatest potential for collecting high-quality data contributing to the decisional needs of prosthesis users. Interview guides will be informed by peer reviewed literature on prosthetic design, the Shared Decision Making Model for Clinical Practice, and the Ottawa Decision Support Framework and contain broad, open-ended questions to explore perspectives on prosthetic decision making.

Focus groups are advantageous when the best information is likely to come from group interaction, and will be conducted with prosthetist participants by a trained qualitative interviewer using video web conferencing with audio recording. Given the professional nature of the decision and environment in which prosthetic design decisions take place, the collaborative group approach within a focus groups will likely provide

optimal high quality, rich data around the decisional needs of prosthetists.

In addition to qualitative data collection, descriptive data will be collected from all recruited participants (prosthetists and patients with LLA), including demographics, the Control Preferences Scale (a measurement of preferences regarding participation in healthcare decisions), and the eHealth Literacy Scale (a measurement of perceived ability to find and use traditional, scientific, media, and computer health information), in order to inform future methods for implementation of the DA.

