# B.2. Aim 1: Qualitative Study Participants and Sampling Plan

Participants (estimated up to 14 patients, within 1 year from lower limb amputation, receiving their first prosthesis and up to 24 prosthetic care providers) will be recruited through well-established clinical partners representing diverse prosthetic practice environments (including the Denver VA Medical Center and private prosthetics practices), located in Albuquerque, NM, Tucson, AZ, and Denver, CO, and clinics throughout the US. Patient participants will also be recruited through the Amputee Coalition of America, and through Amputee List Serve (AMP-L). Standard to qualitative research methods, purposive sampling will be employed to ensure maximum variation of socio-demographic and clinical characteristics, and to ensure inclusion of all key stakeholders in the prosthetic design process.65 Prosthetic care providers will be sampled based on a diverse representation of professional experience and involvement in the prosthetic design process, including prosthetists, therapists, physicians, and associated care providers. Patient participants will be sampled based on diverse representation of above- and belowknee amputation, age, sex, etiology, and availability to participate in a 1-hour, semistructured interview. The patient sample is expected to reflect a distribution of amputation levels and etiologies similar to population-level estimates: ~54% vascular and ~45% traumatic etiology. 66 Patients will be recruited early in their rehabilitation process, for insight into the decisional needs for their first prosthesis and initial care planning. Recruitment will target 14 patients and 24 prosthetic care providers with the goal of achieving thematic saturation, the point where no additional properties of themes emerge from qualitative analysis. 67-69 If thematic saturation has not been attained, enrollment will continue beyond the targets for each group.

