# C.3.2. Aim 2: Developing a DA Prototype

The development of the DA proposed in this study will follow the IPDAS guidelines for decision aid development. Based on this guideline, the DA will include high quality evidence on the options in sufficient detail for each decision associated with prosthetic design, potential outcome probabilities, clarity for identifying patient values associated with each option, and guidance on deliberation and communication. Use of plain language will be implemented and checked by the *expert working group*, for comprehensiveness for all literacy levels. Format of the decision aid will be established (i.e., paper article, video, web-based). For accessibility in multiple environments (long distance vs. local, internet access vs. no technology access), a minimum of two formats will be considered.

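### Aim 1 names only video for the patient interviews and does not sample on technology access, so patients without video are likely to be under-represented

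*Combined protocol and SAP*

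**What the plan says.** The relevant text of the combined protocol and SAP is in four places.

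- **Section IV.A.1, interviews and focus groups.** The patient interviews are to be "conducted by a trained qualitative interviewer using video web conferencing with audio recording". Provider focus groups likewise "will be conducted with prosthetist participants by a trained qualitative interviewer using video web conferencing with audio recording". The reason given is that video keeps the rapport, accuracy and validity of a face-to-face interview "while reducing participant travel burden". No telephone, in-person or clinic-hosted alternative appears anywhere in the document.
- **Section IV.A.1, questionnaires.** "In addition to qualitative data collection, descriptive data will be collected from all recruited participants (prosthetists and patients with LLA"; these are demographics, the Control Preferences Scale and the eHealth Literacy Scale. The last measures "perceived ability to find and use traditional, scientific, media, and computer health information". The stated purpose is to guide later implementation of the aid. How the questionnaires are administered is not stated.
- **Section B.2, sampling.** "purposive sampling will be employed to ensure maximum variation of socio-demographic and clinical characteristics". The patient factors listed are amputation level, age, sex, etiology and availability for a one-hour interview. The target is 14 patients, extended if themes have not saturated.
- **Section C.3.2, format of the aid.** "For accessibility in multiple environments (long distance vs. local, internet access vs. no technology access), a minimum of two formats will be considered".

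**The concern.** The plan regards technology access as relevant to the design of the aid, but the only stated way into a patient interview requires it. Section C.2 makes Aim 1 the source of the decision components, the determinants, the target end users and the necessary content. A group missing from Aim 1 is therefore missing from the foundation on which Aims 2 and 3 build.

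Two things are at stake. The main one is that the decisional needs of patients without video may go unheard. The lesser one is that the eHealth Literacy Scale is given to the same participants. Entry to the patient sample may then depend on an ability related to what the scale measures, which could make the scores look better than those of the patients the aid is meant to reach.

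**Working it through.** **1. The plan has no figure to reproduce.** The 14 patients are a saturation target, not the result of a power or precision calculation. The main check is a comparison of the text.

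| Question | What the document says | Where |
|---|---|---|
| How are patients interviewed? | Video only | IV.A.1 |
| Is there a fallback? | None stated | whole document |
| Is technology access a sampling factor? | Not listed | B.2 |
| Is a setting without technology among those intended? | Yes, at least two formats to be considered | C.3.2 |
| Is interview mode named as a limitation? | No; the convenience-sample limitation is tied to clinic selection and willingness to give feedback | E |

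**2. Would a later step repair the gap?** The saturation rule in B.2 cannot detect it, because themes can saturate among video users while other patients are never heard. The expert working group (B.1) is chosen for expertise and stakeholder representation. Its patient members come from a support group, an advocacy organisation and a list serve, with no criterion on technology access. It may include such patients, but nothing ensures it.

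**3. How many patients might be missed?** Let q be the share of eligible patients who cannot use video. The documents do not give q, so a range is assumed. In a random sample of n = 14 that ignored mode:

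- expected number = 14 × q
- chance of at least one = 1 − (1 − q)^14

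| q (assumed) | Expected of 14 | Chance of at least one |
|---|---|---|
| 5% | 0.7 | 51% |
| 10% | 1.4 | 77% |
| 20% | 2.8 | 96% |
| 30% | 4.2 | 99% |

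If none of these patients can take part, the number is 0. This is the limiting case, since a clinic or helper might supply access. The sample is also purposive, so the table is a benchmark and not a prediction.

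**4. How far might eHealth literacy shift?** Let d be the gap in mean score, in SD units, between patients with and without video (also assumed). The mean over all patients is (1 − q) × mean with access + q × mean without access. A sample drawn only from those with access therefore exceeds it by q × d.

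| q (assumed) | d = 0.25 | d = 0.5 | d = 1.0 |
|---|---|---|---|
| 5% | 0.013 SD | 0.025 SD | 0.05 SD |
| 10% | 0.025 SD | 0.05 SD | 0.10 SD |
| 20% | 0.05 SD | 0.10 SD | 0.20 SD |
| 30% | 0.075 SD | 0.15 SD | 0.30 SD |

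The standard error of a mean of 14 is 1/√14 = 0.27 SD. Only the extreme cell (q = 30%, d = 1.0) exceeds it. The possible loss of these patients' views therefore matters more than the shift in the mean.

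**The case against.** The strongest reply has four parts.

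**No one is excluded.** There is no criterion on technology, patients are recruited partly through clinics, and nothing bars assisted or clinic-hosted video. This stands. A reader might infer that these patients are shut out altogether, but the documents support only that they are likely to be under-represented, because no provision is made for them. Nor is all of Aim 1 shown to be collected by video, since the questionnaire mode is not stated. That does not remove the selection, because the questionnaires go to the same participants.

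**Video has a rationale beyond travel.** Section IV.A.1 cites rapport, accuracy and validity, and the supporting reference is, by its listed title, a comparison of telephone with in-person interviews. This is a fair reason to prefer video to telephone as the default. It does not address a patient who cannot use video, or an interview at the clinic.

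**Format does not depend on Aim 1 scores.** A reader might infer that inflated eHealth literacy would push the study towards a web-only aid. The documents do not support this. C.3.2 already commits to considering two formats whatever the scores show, and no threshold or decision rule uses the scale. Equally, C.3.2 says the formats will be considered, so it is not a firm requirement that the aid work without technology.

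**An upward bias is not shown.** This stands. The direction is a reasonable inference for patients, but there is no evident reason for it among providers, who complete the same scale. The scale also covers traditional, scientific and media information, so it is not simply the entry condition.

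**Conclusion.** The point holds as a gap in coverage. Video is the only stated mode for patient interviews, technology access is not a sampling factor, and C.3.2 names settings without technology as relevant to the aid. Patients in those settings are likely to be under-represented where decisional needs and end users are defined, and neither the saturation rule nor the section E limitation addresses it.

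The size cannot be derived from the documents; the tables above rest on assumed q and d and on complete non-participation. Patient eHealth literacy may be somewhat high, but this is secondary: mostly below sampling error, descriptive, and tied to no decision. The study is low-risk and exploratory, and the gap does not undermine it. It is worth closing because closing it is cheap.

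**What to change.** 1. In section IV.A.1, keep video as the default and add a sentence such as: *Patients who cannot use video will be interviewed by telephone or at a clinic visit, with audio recording and the same interview guide, and will complete the questionnaires by the same route.*
2. Add an interview-mode field to the data form.
3. In section B.2, add technology access to the purposive sampling factors for patients. No fixed quota is needed, because nothing in the documents would justify a particular number.

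The cost is one sentence in IV.A.1, one added factor in B.2 and one data field. The target of 14 and the analysis are unchanged. Recruitment already runs partly through clinical partners, so a clinic option looks practicable. The downside is less rapport and no visual cues in the few interviews held by telephone. If the sponsor prefers video only, section E should at least state that interview mode limits who is heard.
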